## **F. TRAINING**

All study team members have completed the web-based Collaborative IRB Training Initiative (CITI) Program in the Protection of Human Subjects Research. The Project Manager will ensure that all study team members stay current with all required Emory and VA research trainings.

In addition, for all study team members working directly with participants, trainings will be conducted on the administration of structured interviews (CAPS, MINI), informed consent process, psychophysiological data collection, ECG, HRV data collection, phlebotomy (if applicable) and specimen processing. Once the staff member has met all training requirements for each item, they can begin working with study participants.

A detailed log of all study-related trainings will be maintained throughout the study.

## **G. DATA AND SAFETY MONITORING PLAN**

### **Data and Safety Monitoring Plan (DSMP)**

**Safety Monitoring:** The PI or anyone else who has contact with study participants during study activities have the responsibility to monitor for any potential adverse events and protocol deviations. Any potential participant for an adverse event will be reported immediately via “warm transfers” per VA guidelines at respective site and PI, who will contact the participant and determine if additional intervention is needed to ensure participant safety. Study personnel will be trained on these procedures, including contacting VA Police, on-call Mental Health providers Veterans Crisis Line and/or local crisis lines. Protocol deviations will also be immediately reported to respective site PI who will ensure that adverse events deemed to be unanticipated problems and protocol deviations are properly reported to the IRB in a timely manner. Detailed written documentation will be kept for all adverse events that occur over the course of the study. PI will hold regular meetings with study staff where they will discuss adverse events and protocol deviations associated with this project and ways to reduce repeat occurrences. Research staff will examine all cumulative adverse events quarterly to determine if there are any systematic problems and to implement protocol corrections as needed after receiving IRB approval.

**Data Monitoring:** All information linking study data to PHI will be kept within VHA electronically in secure computer files stored behind firewalls requiring password access, or in hardcopy form in locked file cabinets in locked offices. All patient identifiers will be removed prior to analysis. All investigators and team members who will have access to the data will have received appropriate background checks as part of hiring and/or credentialing and will have completed Data Security Training within the prior 12 months.

Per VHA guidelines, data resulting from this study will be stored locally on VHA password-secure folders. Requests for data access will be considered and responded to within one month of the request and datasets will be made available electronically. Requests must be made in writing to the study PI and provide information on the purpose for accessing the data.

All data used in final, published results will be made available for sharing. Published data will be available upon request to any investigator in order to enable independent validation and interpretation of published data.

Once the current study is closed, we will store de-identified, anonymized dataset in an approved data repository consistent with policies in 1200.12 (Use of Data and Data Repositories in Research). A sharing agreement will prohibit the recipient from identifying or re-identifying (or taking steps to identify or re-identifying (or taking steps to identify or re-identify) any individual whose data are included in the dataset.

### **Adverse Event Reporting**

IRB Protocol Version 12

11/23/20

The principal investigator will be responsible for following adverse event reporting requirements as outlined below in the protocol. These responsibilities include: 1) reviewing the accuracy and completeness of all adverse events reported, 2) compliance with local IRB policies for reporting adverse events and/or serious adverse events, and 3) overseeing monitoring of research volunteers at each follow-up visit and as indicated by notification by the yoga teachers at each yoga intervention session. Relatedness involves an assessment of the degree of causality between the study intervention and the event. The PI will perform an assessment of relatedness, in conjunction with [name], who has significant experience in data safety monitoring. All AEs with a reasonable, causal relationship to the intervention will be considered "related." A definite relationship does not need to be established.

### **AE and SAE Monitoring**

For the proposed study, participants will be monitored at each data collection point and as indicated by notification from the yoga/CPT teachers at each intervention session. Adverse events and serious adverse events will be assessed for relatedness to study participation and whether the event was anticipated or unanticipated. Those adverse events found to be unanticipated and related to study participation will be reported to IRB and VA R&D according to local reporting guidelines.

### **Safety Assessments**

Safety assessments will be conducted with any study participant who reports new onset of: suicidal or homicidal thoughts, psychosis, substance use, or physical pain/symptom or physical injury that is determined to require medical evaluation beyond evaluation conducted within the TRP by [name] or her designee.

### **Expedited Reporting of SAEs**

Serious Adverse Events found to be related to participation in the research will be reported to IRB and Atlanta VA R&D according to local reporting requirements.

### **Collaborative Research**

This protocol describes a multi-site study to be conducted at the AVAHCS and the VAPORHCS. AVAHCS is the coordinating center with VAPORHCS recently added as an additional site.

As the primary site/coordinating center, study staff of the AVAHCS will be responsible for equivalent study procedures described in this protocol but conducted in Atlanta. Additionally, AVAHCS study staff will be responsible for assistance in screening for the purposes of recruitment and the storage and analysis of biophysiological data that is collected from participants of VAPORHCS. Where applicable, these tasks have been described as to be conducted at AVAHCS. Project Management of the coordinating center is being conducted by [name] ([[contact]](mailto:[contact]); [contact], [name]).

### **Certificate of Confidentiality**

N/A. The study does not include a Certificate of Confidentiality

### **Disclosure/Sharing**

N/A. The study does not include disclosure/sharing outside the IRB-approved VAPORHCS and AVAHC study personnel.

## Statistical Analysis Post hoc: Equivalence Testing

### Detailed Methods:

While the original RCT was designed for inequality hypothesis testing, given the lack of differences seen between the 2 treatments (both performed well), we additionally conducted equivalence tests of means between the two treatment groups using two one-sided unequal-variance t-tests (TOST). These equivalence tests were performed using the TOSTER v.0.4.0 package for R [REFS Lakens (2017); Lakens, Scheel and Isager (2018)]. The changes from baseline to each follow-up time point were computed for each participant. These change scores were then used to perform two one-sided t-tests (TOST) between the two treatment groups to test for equivalence and reject the presence of the smallest effect size of interest (SESOI). This approach essentially checks to see if the 90% confidence interval bounds for the mean difference between the two groups are within the limits defined by the SESOI. Similar to Sloan, et.al. (2022), a margin of 10 was used as the SESOI. Sloan was only interested in one-side of the margin and performed non-inferiority tests since they assumed one treatment might be inferior to the other. However, we did not have an initial assumption that one treatment would be better than the other, so two one-sided tests or TOSTs were performed to test for equivalence within +/- 10 points. This SESOI was used for both the CAPS-5 and PCL-5 change score differences between the two treatment groups. It has also been suggested that a difference as small as 5 points for the CAPS-5 may be useful for comparing treatments for PTSD so the mean and standard deviation of all changes scores are also reported by group and time for descriptive comparisons. For clinical diagnostic comparisons, similar to Schnurr, et.al. (2022), the percentage of participants at each time point who still have PTSD are reported as well as the percentage who achieved a clinical response (reduction of CAPS-5 severity scores by 10 or more points from baseline), loss of diagnosis (CAPS-5 change  $\leq -10$ , no PTSD diagnosis and CAPS-5 severity score  $< 25$ ), as well as those who achieved remission (loss of diagnosis plus CAPS-5 score  $< 12$ ). All statistical analyses completed using SPSS version 27.0.0.0 [IBM Corp (2020)] and R version 4.1.2 [R Core Team (2021)].

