## **C. STUDY DESIGN AND METHODS**

### **COVID-19 Contingency Plan (Atlanta and Portland)**

As a result of the COVID-19 pandemic, local directive (3/12/2020) suspended study intervention visits for this study and national (3/17/2020) directive suspended all non-essential, in-person visits until further notice. Thus, we have modified the study design and methods to conduct group interventions and data collection virtually when possible. All interview-based assessments will be conducted via a suitable/authorized remote conferencing service between participant and research coordinator, i.e. Zoom Pro. All group intervention sessions will be conducted via a suitable/authorized remote conferencing service with group facilitators and group participants, i.e. Zoom Pro. Participant self-report will be entered by participant via direct entry of fully de-identified data into a secure REDCap web-based application. In the event self-report and/or interview-based assessments cannot be conducted via remote/virtual methods, the assessments will be administered via telephone. Informed consent and HIPAA authorization will be emailed and mailed to potential participants and reviewed via remote conferencing service or telephone. Once signed consent has been received by research

staff, data collection visits and interventions will be conducted in the aforementioned manner. We will suspend collection of in-person physiological data at the Atlanta site. Portland site will utilize mail and drop off/ pick up for data collection kits such as portable KardioScreen ECG machines finger-stick blood collection method, portable BodyGuard HRV devices (Atlanta and Portland). Devices will be cleaned/sterilized in concordance with manufacturer's instructions and CDC guidelines.

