## **Study Intervention**

### **Trauma Center-Trauma Sensitive Yoga**

The yoga intervention consists of a standardized trauma-sensitive Hatha yoga protocol developed by Emerson, Spinazzola and colleagues for use with civilian women with treatment-resistant PTSD. Hatha yoga is a general term to describe the practice of physical postures, breath work, and mindfulness—what is commonly referred to in the West simply as “yoga.” There are many styles of Hatha yoga (e.g., Iyengar, vinyasa, Ashtanga, Bikram), but when the term Hatha yoga is used in the West in contrast to another specified style, it most often designates a more gentle, slower-paced approach to the physical postures. Our protocol uses this gentler, slower approach. It involves ten weekly 90-minute group sessions of Trauma Center-Trauma Sensitive Yoga. Sessions address themes related to establishing safety, individual choice, being in the present moment, and taking effective action. The intervention will be conducted by yoga teachers certified in Trauma Center-Trauma Sensitive Yoga. Study staff will provide participants in the yoga intervention with detailed information related to the sessions. In addition, instructional DVDs will be provided to participants in the yoga intervention to facilitate practice at home. For participants who do not have access to a DVD player, a link will be provided which will direct participants to the private online videos on YouTube. These videos are hidden from the public, therefore the only way to gain access is by entering the link provided by the study team. Finally, reminder calls will be made each week to ensure optimal group attendance. During follow-up visits, study staff will assess whether participant engaged in at-home TC-TSY practice, and the frequency of at-home practice (via use of DVD/online videos, breathing techniques etc.) using an intervention tracking form.

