### **Cognitive Processing Therapy-Cognitive**

The control group, Cognitive Processing Therapy (CPT), is one of the gold-standard therapies for PTSD treatment in the VA mental health system. CPT is a cognitively-based, trauma focused treatment which will be led by two licensed clinical social workers who work in the Women's Trauma Program. As per the treatment protocol, there are twelve 90-minute weekly sessions. The group sessions focus on identifying how thoughts change as a result of trauma exposure and ways in which to realistically evaluate these maladaptive thoughts and come up with more accurate alternative thoughts. Also per protocol, group members do not share their specific trauma details in group. These sessions will be conducted concurrently with the yoga intervention throughout the course of the study. Study staff will provide participants in the CPT group with detailed information related to the sessions. Reminder calls will be made each week to ensure optimal group attendance. During follow-up visits, study staff will assess the degree to which participant engaged in homework assignments and used strategies learned in group using an intervention tracking form.

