### **Data Quality**

All data will be examined for completeness and an assessment of missing data will be performed to check for any biases which may occur. Data will be monitored and entered promptly in order to detect issues as they arise. Special attention will be paid to note what, if any, demographic and clinical factors may be related to subject attrition, retention and adherence. Study retention refers to those who complete all study-related assessments. Dose-effects will be accounted for based on the number of treatment sessions attended by each subject relative to their assigned group. Analyses will be performed to determine what if any covariates may be predictive of missing data over time and these variables will be adjusted for in subsequent models. Close attention will be paid to underlying normality assumptions. Numerical transformations (such as square root, log, and inverse functions) may be applied to correct for deviations due to skewness.

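### The post hoc equivalence test treats women in the same therapy group as independent, so its 90% interval is too narrow if outcomes correlate within groups

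*Combined protocol and SAP*

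**What the plan says.** Under Study Intervention, the yoga arm is group-based: "It involves ten weekly 90-minute group sessions of Trauma Center-Trauma Sensitive Yoga". For CPT, "there are twelve 90-minute weekly sessions. The group sessions focus on identifying how thoughts change as a result of trauma exposure". The COVID-19 Contingency Plan moves delivery online but keeps the group format: "All group intervention sessions will be conducted via a suitable/authorized remote conferencing service with group facilitators and group participants".

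The section on post hoc equivalence testing describes "equivalence tests of means between the two treatment groups using two one-sided unequal-variance t-tests (TOST". The unit of analysis is the individual woman: "The changes from baseline to each follow-up time point were computed for each participant". The procedure "checks to see if the 90% confidence interval bounds for the mean difference between the two groups are within the limits" set by the margin, which is 10 points either way for both CAPS-5 and PCL-5. The section presents these tests as an addition to a trial designed to detect a difference.

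No section mentions a therapy-group term, a cluster-robust error or a design effect. Data Quality says "Dose-effects will be accounted for based on the number of treatment sessions attended by each subject", which concerns attendance, not shared group membership. Statistical Analysis names within-subject and between-subject variance for the mixed models and does not mention a therapy-group level.

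**The concern.** Women who attend the same group share facilitators, fellow members and sessions, so their changes after treatment may be correlated. An unequal-variance t-test lets the two arms have different SDs, but it still assumes that women within an arm are independent. If they are not, the standard error is too small.

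The direction matters here. In a test for a difference that finds none, too narrow an interval usually leaves the negative result standing. In an equivalence test, a narrow interval is what produces the positive claim, so the error favours equivalence.

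**Working it through.** **Inputs from the documents.** Group delivery in both arms (Study Intervention; COVID-19 Contingency Plan). Margin ±10 and 90% interval, so each one-sided test is at 5% (post hoc section). An expected 52 women per arm after 50% attrition (Power Analysis).

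**Assumptions, because the documents give no value.** 52 analysed per arm; m = 3 to 8 analysed women per therapy group (6 to 16 randomized per group if the 50% attrition is spread evenly); ICC 0.01 to 0.10; SD of change 10, 15 or 20 points.

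**The plan's own figure.** Two-sample t-test, 52 per arm, 102 df, d = 0.555, two-sided 5% (assumed, as alpha is not stated). The noncentrality is 0.555 × √(52/2) = 2.83, giving power of 80.0%. The stated figure reproduces and is correct for independent participants. No power or sample size is stated for the equivalence test.

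**Formulas.**
- Design effect: DE = 1 + (m − 1) × ICC.
- Unadjusted half-width: 1.660 × SD × √(2/52), where 1.660 is the 95th percentile of t on 102 df.
- Adjusted half-width: t × √DE × SD × √(2/52), with t on group-based df = 2 × 52/m − 2.
- One-sided error of the unadjusted test at the margin: approximately P(T > 1.660/√DE), T on 102 df.
- Largest observed difference that passes: 10 − half-width.

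| m | ICC | DE | √DE | df | t | Width ratio | One-sided error, unadjusted test | Passing limit, SD 10 / 15 / 20 |
|---|---|---|---|---|---|---|---|---|
| unadjusted | 0 | 1.00 | 1.000 | 102 | 1.660 | 1.00 | 5.0% | 6.74 / 5.12 / 3.49 |
| 3 | 0.01 | 1.02 | 1.010 | 32.7 | 1.693 | 1.03 | 5.2% | 6.65 / 4.97 / 3.29 |
| 5 | 0.05 | 1.20 | 1.095 | 18.8 | 1.730 | 1.14 | 6.6% | 6.28 / 4.42 / 2.57 |
| 8 | 0.10 | 1.70 | 1.304 | 11 | 1.796 | 1.41 | 10.3% | 5.41 / 3.11 / 0.82 |

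Example, last row at SD 15: 10 − 1.796 × 1.304 × 15 × 0.1961 = 10 − 6.89 = 3.11.

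The √DE column is the widening from the design effect alone, 1.01 to 1.30. The width ratio adds the loss of df, giving 1.03 to 1.41.

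**Simulation check.** The unadjusted test at SD 15, with 300,000 runs per setting, gave a one-sided error at the margin of 5.2%, 6.7% and 10.5% for the three clustered rows. At ICC 0 it gave 4.9% to 5.1%, so the excess comes from clustering.

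**When a verdict would change.** The observed difference would have to lie between the adjusted and unadjusted passing limits. From the first to the last clustered row, that band grows from about 0.1 to 1.3 points (SD 10), 0.15 to 2.0 (SD 15) or 0.2 to 2.7 (SD 20).

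**The case against.** The strongest reply is that the size of the problem rests on assumptions. With small groups and a low ICC the one-sided error moves from 5% to 5.2%, and the 10% figure needs the largest assumed group and the largest assumed ICC together. The error rates also apply only when the true difference is exactly 10 points, whereas the tests were added because little difference had been seen. With an observed difference near zero, every setting in the table still passes. All of this stands. It limits how much weight the point can bear, but the interval still rests on an independence assumption that nobody has checked.

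A reader might infer more in three ways, and the documents support none of them:
- **That the equivalence result is wrong or would reverse.** The section states no equivalence conclusion, and the documents give no results, SDs or group sizes.
- **That the mixed models under Statistical Analysis are misspecified.** That section neither names nor excludes a therapy-group level; silence is not an error.
- **That the power calculation is wrong.** It reproduces exactly under independence and needs no correction.

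It is also fair to say that the documents do not establish that groups were closed cohorts. If membership was rolling, a simple group term would need adapting.

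**Conclusion.** The point holds in conditional form and is confined to the post hoc equivalence test. Both arms are group-delivered, the test works on individual women, and no section allows for correlation within therapy groups. If the ICC is above zero, the interval is too narrow in the direction that favours equivalence. For the assumed 52 per arm, 3 to 8 analysed women per group and ICC 0.01 to 0.10, the properly adjusted interval is 1.03 to 1.41 times as wide with group-based df. For most plausible small-group settings the inflation of error is modest, and the top values come from one corner of the range. Whether any reported verdict is affected cannot be told from the documents. This is an inexpensive improvement to a supplementary analysis, not a defect shown to alter a conclusion.

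**What to change.** In the post hoc section, keep the unadjusted test and report beside it a 90% interval from an analysis that allows for therapy group: a random intercept for therapy group nested in arm with small-sample df, or a t-test on group means. Adapt the model if groups were rolling or women changed groups. Report the number and size of groups and the estimated ICC, noting that it will be imprecise. If cohort membership cannot be recovered, show the interval over a range of ICCs and state the limitation. Using the same term in the main mixed models would be consistent, but is only a suggestion.

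The cost is reanalysis, with no new data from participants. Data Management mentions session sign-in sheets; that they identify cohorts is an inference. The statistical price is a wider interval and some lost power when the ICC is near zero. From df alone, the interval widens by 1.693/1.660 = 1.02 at 3 per group or 1.796/1.660 = 1.08 at 8 per group. In simulation at ICC 0 and SD 15, the chance that truly equal treatments pass ±10 fell from 92% to about 89% with a random intercept (13 groups of 4 per arm), or 86% to 91% with group means. Across the simulated layouts and ICCs of 0 to 0.10, the random-intercept variance was estimated as zero in 11% to 55% of runs, so a zero estimate should not be read as proof of independence.

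One limit remains. The CPT section describes an arm "which will be led by two licensed clinical social workers". If the same leaders ran every group in an arm, their effect is shared by all those groups, and a group intercept would not capture it.

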### **Power Analysis**

Given the estimated final sample size of 104 (52 per group) after expected levels of attrition (50% attrition from 210), we will be powered at 80% to detect moderate effect sizes for any differences between the groups (two-group independent t-tests effect size (Cohen's d) of 0.555 and chi-square tests for differences in proportions between the two-groups effect size (Cohen's omega,  $\omega$ ) 0.274 and higher) as well as moderate-to-large effect sizes detected for differences between the groups over time (repeated measures group-by-time interaction effects: effect size of 0.28, Cohen's f) will be detected. Power analyses will be completed using PASS v.13.0.8.

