### **Statistical Analysis**

Comparisons between the groups at baseline will be run using t-tests, Mann Whitney non-parametric tests, and chi-square tests as appropriate. However, when numerical transformations are not sufficient, non-parametric and generalized non-normal response functions may also be employed. Multilevel mixed models (MLM) will be used instead of repeated-measures analysis of variance (RM-ANOVA), to analyze the differences between the groups over time. As opposed to RM-ANOVA which assumes independence between time points and assumes complete data for all subjects at all time-points, MLM adjusts for attrition (missing data) over time and applies appropriate correlation structure between the time points. Multilevel modeling also provides insight into the variance components of the outcomes relative to those related to within-subject variability over time and those related to between-subject differences. These variance components are important for understanding the utility of each measure relative to reliably assessing each outcome. Generalized functions of these MLM models may also be run for non-normal outcomes due to highly skewed or zero-inflated data (common with biomarker and some behavioral measures) or binary outcomes (e.g. diagnosis determinations). These statistical modeling approaches will be applied appropriately to the outcome measures of interest for each of the three research aims. SPSS Version 22.0 will be used for all statistical analyses.

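### The post hoc equivalence test uses unadjusted change scores; a baseline-adjusted mixed-model contrast against the same ±10 margin should be reported beside it

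*Combined protocol and SAP*

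**What the plan says.** The section on post hoc equivalence testing describes the data and the test in two sentences: "The changes from baseline to each follow-up time point were computed for each participant", and then "These change scores were then used to perform two one-sided t-tests (TOST) between the two treatment groups". The tests are unequal-variance t-tests, read through a 90% confidence interval against ±10 points. The margin serves two scales: "This SESOI was used for both the CAPS-5 and PCL-5 change score differences between the two treatment groups". A smaller figure is mentioned but used only descriptively: "It has also been suggested that a difference as small as 5 points for the CAPS-5 may be useful for comparing treatments for PTSD". The section names no covariate, imputation or missing-data rule, and it does not provide for numbers analysed.

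Section E of the protocol reasons differently about missing data:
- Statistical Analysis prefers multilevel mixed models because repeated-measures ANOVA "assumes complete data for all subjects at all time-points, MLM adjusts for attrition (missing data) over time".
- Data Quality says analyses will find which "covariates may be predictive of missing data over time and these variables will be adjusted for in subsequent models".
- Power Analysis plans for 104 women "after expected levels of attrition (50% attrition from 210").

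Table 1 schedules CAPS-5 and PCL-5 at baseline, mid-treatment, two weeks and three months after treatment.

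**The concern.** A change score needs both of its values. Without imputation, a woman with no three-month score drops out of the three-month test, and her mid-treatment score is not used. That gives up the feature for which the protocol chose mixed models, in a trial that planned for heavy attrition. The section states an equivalence margin but never compares a mixed-model contrast with it.

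Two things are at stake. One is precision: the interval may be wider than it need be. The other is bias: in an equivalence test, bias towards zero favours the claim of equivalence, so dropout handling can matter more than it does in a test of difference.

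**Working it through.** **1. The plan's own figure.** With 52 per arm and a two-sided 0.05 level (assumed; not stated), the noncentral t gives power 0.800 at d = 0.555, as stated. Attrition agrees within rounding: 210 × 0.5 = 105. No power is given for the equivalence test.

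**2. Precision from baseline adjustment.** Let s0 and s1 be the baseline and follow-up SDs and ρ their correlation. None is in the documents; all are assumed here.
- Change score: variance = s0² + s1² − 2ρ·s0·s1
- Baseline-adjusted: variance = s1²(1 − ρ²)
- Difference = (s0 − ρ·s1)², never negative, so in large samples adjustment cannot widen the interval.

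The entries show how much narrower the 90% interval becomes:

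| ρ | SDs equal: 1 − √((1+ρ)/2) | s0 = 9, s1 = 12 | s0 = 8, s1 = 12 |
|---|---|---|---|
| 0.3 | 19% | 160.2 to 131.0: 10% | 150.4 to 131.0: 7% |
| 0.5 | 13% | 117 to 108: 4% | 112 to 108: 2% |
| 0.7 | 8% | 73.8 to 73.4: 0.2% | 73.6 to 73.4: 0.1% |

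The last two columns matter because PTSD is required for entry, which may restrict baseline spread.

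Mid-treatment scores can add more. In simulation with equal SDs and random 50% dropout, using them as well narrowed the interval by 15 to 25% in total over five correlation sets. In one set the SE was 2.57 for change scores, 2.16 with baseline and 1.94 with mid-treatment scores too.

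**3. Does precision change the verdict?** Take 52 per arm, SD 12 at both visits and ρ = 0.5.
- Change score: SD 12, SE = 12 × √(2/52) = 2.353, half-width 1.66 × 2.353 = 3.91.
- Adjusted: SD = 12 × √0.75 = 10.39, SE = 2.04, half-width about 3.4.

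With no true difference, the chance of passing is about 2Φ(m/SE − 1.645) − 1. At m = 10 it is 0.991 against 0.999. At m = 5, which the section does not test, it is 0.37 against 0.58.

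**4. Bias from dropout.** Simulation with 105 per arm, SD 12, correlations 0.5 (baseline–mid), 0.7 (mid–post) and 0.4 (baseline–post), 50% dropout unless stated, and 3,000 to 5,000 trials per scenario. Dropout depends on response in one arm only; odds ratios are per 12 points. False equivalence is the pass rate at a true difference of 10 (nominal 5%). A dash means not tabulated.

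| Dropout depends on | Change score: bias; false equivalence | Model: bias; false equivalence |
|---|---|---|
| Mid-treatment change, OR 1.65 | 2.3; 22% | under 0.1; 4–6% |
| Mid-treatment change, OR 2.7 | 4.0; 47% | under 0.1; 4–6% |
| Same two odds ratios, 20% dropout | 0.9 or 1.7; 11% or 21% | under 0.1; 4–6% |
| As OR 2.7, half of dropouts leave before mid | –; 47% | 0.9; 12% |
| As OR 2.7, all leave before mid | –; 48% | 2.6; 33% |
| Unseen final score, OR 2.7 | 2.9; 31% | 2.6; 39% |
| Same, all correlations 0.5 | 2.5; 29% | 3.4; 54% |
| Unseen final change, OR 2.7 | –; 77% | –; 39% |

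Reversing the sign of the dependence in the OR 2.7 case gives a change-score bias of 4.0 points away from equivalence and false equivalence of 0.1%. With the same dependence in both arms and no true difference, change scores are about unbiased.

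**The case against.** The strongest reply is that little turns on this. The equivalence test is disclosed as additional and post hoc, and the mixed-model analysis is not withdrawn. Data Quality also plans an assessment of missing data for bias. At margin 10, precision would rarely alter the result, and the 5-point figure is descriptive only. The gain from baseline adjustment nearly vanishes if baseline spread is restricted. The bias needs response-related dropout that differs between arms (or truly different arms), and the mirror-image pattern makes the test conservative. The 50% is a planning figure. Retention is defined as completing all assessments, so missingness at any one visit may be lower.

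All of that stands, and it limits the size of the point. It does not remove it: nothing in the documents sets the margin against an analysis that uses the partial records, and without numbers per arm and visit a reader cannot judge whether dropout matters.

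Three stronger readings are tempting:
- A reader might infer that the equivalence result is biased or wrong. The documents give no SDs, correlations or dropout by arm, so bias is possible but not shown.
- A reader might infer that the planned analysis was replaced. The section says the tests were added to it.
- A reader might infer that a mixed model would settle the question. The simulations show otherwise when women leave before mid-treatment or when dropout depends on unseen scores.

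**Conclusion.** The point holds as a cheap improvement. The change-score test is valid as a disclosed post hoc analysis, but it leaves out the planned approach to attrition.

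- **Precision:** the adjusted contrast is at least as precise in large samples. The gain from baseline alone is about 8 to 19% under equal SDs and 0 to 10% under restricted baseline spread. At margin 10 and SD 12 this alone is unlikely to change the conclusion.
- **Bias:** if dropout is missing at random and its dependence on response differs by arm, the change-score contrast may be off by about 1 to 4 points, towards or away from false equivalence. The model removes this only when the predictive scores were observed. In the assumed one-arm case its bias is 0.9 if half of dropouts leave before mid-treatment and 2.6 if all do. Under some not-at-random dropout it is the worse of the two.

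Neither analysis is better under every mechanism, which is the reason to show both. All SDs, correlations and dropout patterns here are assumptions.

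**What to change.** In the post hoc equivalence section, add for CAPS-5 and PCL-5 the arm contrast and 90% interval at each follow-up visit, against the same ±10 margin, from a mixed model with:
- arm by visit, with baseline as a covariate or a common baseline, and a stated covariance structure;
- all randomised women with any data, analysed as randomised;
- only pre-randomisation covariates. Data Quality also says: "Dose-effects will be accounted for based on the number of treatment sessions attended by each subject relative to their assigned group". Attendance is measured after randomisation and should not enter this model as a covariate.

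Present it beside the change-score test, label both post hoc, give numbers analysed per arm and visit, and discuss any disagreement.

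A tipping-point analysis is a useful option: shift the unobserved scores in one arm until the interval crosses the margin. For scale, at an estimate of 0, an SE of 1.94 and 50% missing, the shift is (10 − 1.66 × 1.94)/0.5, about 14 points.

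Requiring both analyses to pass is not part of the fix. It lowers false equivalence to about 2% under random dropout, but in the OR 2.7 missing-at-random case it cuts power to about 76%, against over 99% for the model alone.

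The cost is modest extra modelling of scores already collected, and a second analysis chosen after results were known.
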